The MLC spinal anesthesia protocol included 500cc of isotonic crystalloid solution for vascular filling, bupivacaine 7 to 10 milligrams (depending on the patient's height), morphine 100 micrograms, and sufentanil 10 micrograms.

The FAUCS spinal anesthesia protocol included no vascular filling, no morphine, bupivacaine 7 to 10 mg (depending on the patient's height), and sufentanil 10 micrograms.

A bladder catheterization was performed on the MLC group by using a 16 or 18-F catheter prior to the skin incision. In both groups, a single dose of a first-generation cephalosporin was administered intravenously.

All FAUCS surgeries were performed by two senior surgeons ([name] and [name]). Both were experienced with the paravesical approach and had performed more than 30 cases previously. The MLC cesarean operations were performed by same seniors or residents who performed vast majority of the operations in the unit.

For this study, we performed the MLC technique as described in 1999 ³.Regarding the FAUCS approach described in 2017, the use of skin glue for closure is recommended ⁶. In order to

ensure that all the patients were virtually indistinguishable, we alternatively employed a subcuticular absorbable Vicryl suture for the skin closure.

Hematocrit levels were assessed before and after surgery. Analgesics were administered by the nursing staff, upon patient's requests and visual analogue scale (VAS)⁸. Assessments with VAS were made every 6 hours: H0,H6,H12,H18, and H24. A standardized analgesics scheme was used:

First intention: 100 mg Ketoprofen intra-rectal route every 6 hours.

Second intention: intra venous1g paracetamol every 6 hours.

Third intention: tramadol 50 mg oral route every 6 hours.

A first standing was proposed to all women everyhour during the first post operative day.

The bladder catheter was removed as soon as the woman was able to walk alone.Normal oral food intake was initiated as soon as gas passage occurred and the patient felt hungry.

Women were evaluated by the end of the first day. If there were no complications and if the patient felt autonomous and pain-free, they were discharged 24 hours after the surgery. In the other cases, patients were discharged at least 48 hours after surgery after a similar evaluation of maternal autonomy.

The primary outcome measure of the study was the post-operative mean pain score (PMPS).

PPMS = (VAS H0+ VAS H6 + VAS H12+ VAS H18 + VAS H24)/5.

Secondary Outcome Measures were:

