- VAS max : defined as the highest post operative pain score felt during the first day.
- Total dose of administrated analgesics during the first 24 hours (mg).

- Calculated estimation of blood loss (cEBL): derived by multiplying the calculated maternal blood volume by the percent of blood volume lost, were the maternal blood volume was calculated by Nadler's formula based on the patient's weight, and height. The percent of blood volume lost was calculated with Brecher's formula⁹ [$\{(\text{predelivery hematocrit (HCT)} - \text{post delivery HCT})/\text{predelivery HCT}\}$].
- Surgery time in minutes: T1: Delay between skin incision and hysterotomy; T2: Delay between hysterotomy and fetal extraction (min); T3: time spent for uterine sutures; T4: total duration of the surgery.
- Rate of short-term incidents: hemorrhage, transfusion, bladder injury or any other complication.
- Maternal autonomy: time to first spontaneous urination, time to first standing; time to first complete meal.
- Newborn overall condition: Neonatal acid base balance (Cord blood gases, pH and eucapnic pH¹⁰; Apgar score at 1 and 5 minutes after birth, rate of neonate hospitalization.
- Delay to hospital discharge (days).

Statistics

The sample size (N) calculations were based on the post-operative mean pain score (PMPS) as the main outcome measure. The mean (m_1) and standard deviation (σ) for the PMPS in the MLC group were estimated by reviewing the records of 80 consecutive women who underwent this procedure in 2017. These values were approximately $m_1=3.8$; $\sigma=2$. We aimed to detect a decrease of 60% in the PMPS in the FAUCS group (m_2), taking into account the level of significance ($p=.05$) and the expected power of the study (80%), with $\alpha=0.05$ and $\beta=0.10$; we used the following formula: $N = M / D_s^2 \cdot M = 2 * (z_{1-\alpha} + z_{1-\beta}) = 17.1$; $D_s = (m_1 - m_2) / \sigma$; $N = 17.1 / (0.6 m_1 / \sigma)^2$. 45 patients per group were required to detect a

decrease of 60% in PMPS scores between the two groups. Ultimately, we recruited 50 participants for each group to account for possible losses.

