We measured 44 outcome variables. The metrics were grouped into four categories: surgery, overall morbidity, neonatal outcomes and maternal autonomy during recovery. All the analyses were conducted in RStudio (version 3.5.1). We performed unequal variance t-tests for all continuous variables and evaluated each distribution for normality using the Shapiro Wilk test. Continuous variables were analyzed with the student's t test and Mann-Whitney test. We performed asymptotic generalized Pearson's chi-squared tests for the categorical variables. When the categorical variables were ordinal, we used the Cochran-Armitage test, comparing one ordinal variable with a dichotomous one. All tests were performed as 2-tailed tests, and $p < .05$ was accepted as statistically significant.

To visualize the results, we employed smoothed kernel density plots of continuous outcome variables for FAUCS compared with the MLC values, which were viewed on a log scale where applicable.

5. S BD, J C. Extraperitoneal versus transperitoneal cesarean section in surgical morbidity in a tertiary care centre. *Int J ReprodContraceptObstet Gynecol.* 2017 Jul 26;6(8):3397–9.

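### Analgesic use is defined as one 24-hour total in mg; read as a sum over the three drugs, it is governed by paracetamol, so each drug should be reported separately

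*Combined protocol and SAP*

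**What the plan says.** The list of secondary outcome measures contains one item on analgesic consumption: "Total dose of administrated analgesics during the first 24 hours (mg"). It names no drug, and does not say whether drugs are added together or converted to a common scale.

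The analgesic scheme appears earlier in the Study Protocol text. "Analgesics were administered by the nursing staff, upon patient's requests and visual analogue scale" (VAS), in three steps:

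- first step: "100 mg Ketoprofen intra-rectal route every 6 hours";
- second step: 1 g of intravenous paracetamol at the same interval;
- third step: "tramadol 50 mg oral route every 6 hours".

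The Statistics section sends continuous variables to t-tests and the Mann-Whitney test, and adds no rule for this outcome. It also states "We measured 44 outcome variables", without a list.

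**The concern.** A milligram of ketoprofen, of paracetamol and of tramadol are not interchangeable quantities. Adding them gives each drug a weight set by its tablet or vial strength: one paracetamol dose counts as 10 ketoprofen doses (1000/100) or 20 tramadol doses (1000/50). Because dosing followed request and pain score, the mix of drugs can differ from woman to woman and from arm to arm.

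The primary outcome is a pain score, so analgesic consumption is the natural companion result: a reader will use it to judge whether lower scores were obtained with less or with more medication. If the figure is a pooled total, a statement that one technique needed less analgesia could rest almost entirely on paracetamol, and the reader could not tell.

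**Working it through.** The plan states no figure for this outcome, so there is none to reproduce. The check is arithmetic on the protocol's own scheme.

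**Inputs** (analgesic scheme, Study Protocol text): ketoprofen 100 mg, paracetamol 1000 mg, tramadol 50 mg, each every 6 hours. That is m = 4 doses of each drug in 24 hours, or m = 5 if doses at both H0 and H24 are counted. "Ultimately, we recruited 50 participants for each group" gives the arm size.

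**Pooled total.** For k, p and t doses of the three drugs, total = 100k + 1000p + 50t.

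**Ordering of two women.** Suppose one woman had at least one more paracetamol dose than another. The most the other can make up is m × (100 + 50).

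| Doses per drug | Largest ketoprofen + tramadol | One paracetamol dose | Smallest remaining gap |
|---|---|---|---|
| 4 | 4 × 150 = 600 mg | 1000 mg | 400 mg |
| 5 | 5 × 150 = 750 mg | 1000 mg | 250 mg |

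The woman with more paracetamol always has the larger total. Listing every combination of 0 to m doses confirms it: of 6,250 pairs that differ in paracetamol with m = 4, and 19,440 with m = 5, none is reversed or tied. The ordering first fails at m = 7 (7 × 150 = 1050 mg), which a 6-hourly scheme does not reach in 24 hours. Women with equal paracetamol doses are still ordered by the other two drugs.

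For example, four ketoprofen plus four tramadol doses without paracetamol total 600 mg, and rank below a single paracetamol dose at 1000 mg. This bears directly on the Mann-Whitney test, which uses ranks.

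**Difference in means.** The between-arm difference is 100 × (difference in mean ketoprofen doses) + 1000 × (difference in mean paracetamol doses) + 50 × (difference in mean tramadol doses). In an arm of 50, five paracetamol doses in all (5 × 1000 = 5000 mg) weigh as much as one ketoprofen dose for every woman (50 × 100 = 5000 mg). With equal numbers of doses of the three drugs, paracetamol makes up 1000/1150 = 87% of the total. The t-test is therefore also dominated by paracetamol wherever its use varies.

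**Spinal opioids.** If the total also counted the spinal morphine of the MLC group (0.1 mg) and sufentanil (0.01 mg), the bounds would become 600.11 and 750.11 mg. Nothing changes.

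**Are per-drug totals planned elsewhere?** The named outcomes come to about 22: mean pain score, maximum VAS, analgesic total and blood loss (4); four surgery times (4); four incident types (4); three autonomy times (3); cord gases, pH and eucapnic pH (3); two Apgar scores (2); neonatal hospitalization and discharge (2). The count is rough, since cord gases may be several variables. It leaves room among the 44 for per-drug totals, but the text does not mention any.

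**The case against.** The strongest reply is that summation is inferred. A total dose in mg could also mean a 24-hour total for each drug, and such totals may sit among the unlisted variables. This stands as a limit: a reader might infer that the trial did analyse a meaningless sum, and the documents do not show that. They do show one outcome with one unit, which taken literally is a sum across drugs.

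The second reply is that paracetamol is the second step, so ordering by paracetamol largely orders women by whether they went beyond the first step. This also stands. A woman given ketoprofen only has at most 400 mg (500 mg with five doses), always below a woman who had any paracetamol. If earlier drugs are continued and every step reached is given in full, the total follows the scheme: 400, then 4400, then 4600 mg.

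A reader might go further and infer that the total ranks women wrongly by need. For instance, seven doses as 4 ketoprofen + 2 paracetamol + 1 tramadol make 2450 mg, while seven doses as 4 ketoprofen + 3 paracetamol make 3400 mg, so the woman who reached the third drug ranks lower. The documents do not support calling this an error. They nowhere make the highest step the measure of need, and they do not say whether earlier drugs were continued or when a later one could start. The example shows how the weights work; it does not measure bias.

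**Conclusion.** The point holds as a low-severity matter of outcome definition. On the literal reading, paracetamol alone orders any two women who differ in it, with a margin of at least 400 mg (250 mg with five doses), and a difference between arms would mainly reflect paracetamol use. This rests on two assumptions: that the total adds the three drugs, and that doses were given within the 6-hourly scheme.

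The effect on the result cannot be sized, because no usage data are given. If few women went beyond ketoprofen, the total is mostly one drug and the effect is small. A reader might also infer that the total favours one technique; nothing in the documents indicates a direction. The primary outcome and the sample size are untouched.

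**What to change.** State whether the total adds the drugs. Report, by arm, the 24-hour mg or number of doses of each drug separately, as descriptive figures, and draw no conclusion about analgesic need from a pooled mg total. The highest step reached (none, first, second, third) may be shown as an optional descriptive supplement. If per-drug totals are already among the 44 variables, naming them is enough.

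Recruitment is described in the past tense, so keep the stated total visible and label the additions post hoc if data have been seen.

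The cost is a few more reported figures: three drugs in two arms, plus the step table if used. Keeping them descriptive avoids adding up to four unadjusted tests (three drugs and highest step) to 44 outcomes tested at p < .05. The change requires that doses were recorded by drug, which is plausible but not stated.

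### The cEBL formula has no term for transfused red cells, so it understates blood loss for any woman transfused before the post-delivery hematocrit

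*Combined protocol and SAP*

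**What the plan says.** The secondary outcome list defines cEBL as a product of two quantities: it is "derived by multiplying the calculated maternal blood volume by the percent of blood volume lost". For the first, "the maternal blood volume was calculated by Nadler's formula based on the patient's weight, and height". For the second, "The percent of blood volume lost was calculated with Brecher's formula", and the expression is printed in full: predelivery HCT minus post-delivery HCT, divided by predelivery HCT. No transfused volume enters either factor.

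The same list includes "Rate of short-term incidents: hemorrhage, transfusion, bladder injury or any other complication". Transfusion is therefore an event that the plan provides for, although no anticipated rate is given.

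On sampling, the study protocol text says only: "Hematocrit levels were assessed before and after surgery". It gives no hour and does not place the second sample relative to any transfusion.

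The Statistics section says: "Continuous variables were analyzed with the student's t test and Mann-Whitney test". It has no correction, exclusion or sensitivity analysis for transfused women.

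**The concern.** A fall in hematocrit measures red-cell loss only if no red cells are added between the two samples. Transfused cells raise the second hematocrit, so the formula nets the treatment against the bleeding. The plan names transfusion as an outcome yet applies the same formula to every woman.

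At stake is the only continuous blood-loss measure among the listed secondary outcomes, in a trial that compares two surgical techniques. The error is always downward. For a transfused woman it can be large enough to place her below someone who bled less. If such transfusion were more common in one arm, that arm's cEBL would be lowered more.

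**Working it through.** The documents give no figure for cEBL, blood loss or transfusion rate, so there is no stated result to reproduce. The check carries the plan's own formula through a red-cell balance.

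**Inputs from the documents**
- cEBL = BV x (pre - post)/pre, with BV the calculated blood volume and pre and post the two hematocrits (secondary outcome list).
- Arm size 50, used only to scale the effect on a mean: "we recruited 50 participants for each group to account for possible losses" (Statistics).

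**Assumptions, not in the documents**
- Red cells per transfused unit: 150 to 220 mL, with 180 mL for the worked case.
- Predelivery HCT: 0.36, varied from 0.33 to 0.39.
- BV 5000 mL and true loss 1500 mL in the example.
- Blood is lost at the predelivery HCT and volume is restored by the second sample. With no transfusion, these are the conditions under which the plan's formula returns the true loss.

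**Algebra.** Let L be the true loss and R the red-cell volume transfused before the second sample.
- post = (BV x pre - L x pre + R)/BV
- cEBL = BV x (pre - post)/pre = L - R/pre

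The shortfall is R/pre, whatever the values of BV and L. It is zero when R = 0.

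**Per unit at HCT 0.36**
- 150/0.36 = 417 mL
- 180/0.36 = 500 mL
- 220/0.36 = 611 mL

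Over HCT 0.33 to 0.39, the extremes are 150/0.39 = 385 mL and 220/0.33 = 667 mL.

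**One woman.** True loss 1500 mL, two units of 180 mL before the second sample:
- post = (5000 x 0.36 - 1500 x 0.36 + 360)/5000 = (1800 - 540 + 360)/5000 = 0.324
- cEBL = 5000 x (0.36 - 0.324)/0.36 = 500 mL

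An untransfused woman who lost 600 mL scores 600 mL, so the order of the two is reversed. With three units of 200 mL, the first woman scores 1500 - 600/0.36 = -167 mL, an impossible loss that also cannot be plotted on the log scale that the Statistics section allows for its density plots.

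**Arm mean, 50 women**
- One woman given two units of 180 mL: 1000/50 = 20 mL too low.
- The same at 150 and 220 mL per unit: 300/0.36/50 = 17 mL and 440/0.36/50 = 24 mL.
- Three women given two units of 180 mL: 3000/50 = 60 mL too low.

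**Mann-Whitney, 50 per arm.** SD(U) = sqrt(50 x 50 x 101/12) = 145. One woman who drops from the very top to the very bottom moves U by at most 50, or 50/145 = 0.34 SD.

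**The case against.** The strongest reply is that the problem may never arise or may hardly matter. Cases are elective and at term, adherent placenta is excluded, and women who needed emergency surgery were removed before randomization, so transfusions may be few or none. The error also needs a transfusion before the second sample, and the plan does not say when that sample was taken. If the SD of cEBL is assumed to be 300 to 500 mL, the standard error of the difference is SD x sqrt(2/50) = 60 to 100 mL, so a 20 mL shift is 0.2 to 0.33 of a standard error. The effect on the rank test is similarly limited. cEBL is one of 44 outcome variables, the primary pain score is untouched, and transfusion is reported separately, so a reader could see whether it occurred.

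All of this stands as a limit on size. It does not remove the fault: for a case that the plan itself lists, the printed rule returns a wrong value, and nothing elsewhere in the documents handles it.

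A reader might also infer more than the documents support:
- **That transfusion was expected.** It is listed as an outcome, with no rate.
- **That the error falls on the women who bled most.** No transfusion criterion is stated. A heavy bleeder who was not transfused, or was transfused after the sample, is unaffected. A woman with a low starting hematocrit could be transfused after an ordinary loss.
- **That the arms would reverse, or that cEBL and transfusion rate would conflict.** No between-arm difference or SD is given, so neither is shown. Bias in the comparison requires such transfusion to differ between arms.
- **That the transfused volume is already on record.** The documents list only a rate of transfusion.

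**Conclusion.** The point holds in a limited, conditional form. For a woman transfused before the post-delivery hematocrit, the cEBL formula understates loss by transfused red-cell volume divided by predelivery HCT. The per-unit size of 417 to 611 mL depends on the assumed red-cell content and HCT; the direction does not, given restored volume. This is large for the woman concerned and can reverse her rank against women who bled less.

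For the trial, the effect is probably small. At about 20 mL on an arm mean per two-unit woman, several such women, unevenly split between arms, would be needed for a material bias. With no transfusion before the sample there is none. It is worth correcting because a stated formula gives a wrong answer in a foreseen case, but it concerns a secondary outcome and leaves the primary analysis and the sample size alone.

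**What to change.** 1. Define cEBL = BV x (predelivery HCT - post-delivery HCT)/predelivery HCT + (red-cell volume transfused before the second sample)/predelivery HCT, and state the assumed red-cell volume per unit. In the worked case this gives 500 + 360/0.36 = 1500 mL, the true loss. Untransfused women's values do not change.
2. Record the units given and the time of the post-delivery hematocrit relative to any transfusion.
3. Report the number of women corrected in each arm.
4. Add a sensitivity analysis that ranks women transfused before the sample as the highest losses in the Mann-Whitney test. It needs no volume per unit, but it would rank too high a woman transfused mainly for a low starting hematocrit, so it should stay a sensitivity analysis.

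The cost is one term in the formula, an assumed volume per unit, and data on units and timing that the documents do not say were collected. If no woman was transfused before the second sample, one sentence saying so settles the point.

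### Blood loss (cEBL) is compared without adjusting for predelivery hematocrit or blood volume, both already collected; the test is valid but probably gives up a modest amount of precision

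*Combined protocol and SAP*

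**What the plan says.** The list of secondary outcome measures defines cEBL as "derived by multiplying the calculated maternal blood volume by the percent of blood volume lost". The first factor comes from baseline body size: "the maternal blood volume was calculated by Nadler's formula based on the patient's weight, and height". The second is (pre HCT − post HCT)/pre HCT. The Study Protocol section confirms that both readings exist: "Hematocrit levels were assessed before and after surgery".

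For the comparison, the Statistics section says "We performed unequal variance t-tests for all continuous variables" and, shortly after, "Continuous variables were analyzed with the student's t test and Mann-Whitney test". It adds: "All tests were performed as 2-tailed tests". No regression, ANCOVA or other covariate adjustment is named for cEBL or for any other outcome, and no confidence interval is mentioned.

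The sample size rests on the pain score alone. On that basis "we recruited 50 participants for each group to account for possible losses". cEBL has no power statement, SD or target difference of its own.

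**The concern.** Dividing a change by its baseline does not make it independent of that baseline. If predelivery hematocrit is measured with error, a woman with a chance high reading tends to show a lower second reading, and the formula counts the fall as blood loss. Blood volume multiplies the whole expression, so larger women have larger cEBL for the same proportional fall. Both are sources of variation that the trial already records and could take out of the comparison.

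The stake is efficiency. Leaving in explainable variation may give a wider interval than the data need. In a single trial of about 50 per arm, a chance difference in predelivery hematocrit can also move the blood-loss estimate. The plan describes allocation from a random-number table and no stratification, so the design does not specifically balance hematocrit or body size.

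**Working it through.** **No plan figure to reproduce.** The documents give no mean, SD, correlation or power for hematocrit or cEBL. The planned group size concerns the pain score and does not bear on this point. From the documents I use only the cEBL formula and 50 women per arm.

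**Assumed inputs.** Pre and post hematocrit means 35 and 31, SD 3 each, blood volume 4700 mL (SD 500) independent of hematocrit, and pre-post correlation ρ from 0.4 to 0.9.

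**Slope of cEBL on predelivery hematocrit (first order).** Slope ≈ 4700 × (31/35² − ρ/35) mL per point.
- ρ = 0.5: 4700 × (0.02531 − 0.01429) = 52 mL
- ρ = 0.7: 25 mL
- ρ = 0.9: −2 mL

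The slope is zero at ρ = 31/35 = 0.89.

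**Variance at ρ = 0.5, by hand.** Let R = (pre − post)/pre, with mean about 4/35 = 0.114.
- Var(R) ≈ (31/35)² × [(3/31)² + (3/35)² − 2 × 0.5 × 9/(31 × 35)] = 0.7845 × 0.00842 = 0.0066
- Var(cEBL) ≈ 4700² × 0.0066 + (500 × 0.114)² + 500² × 0.0066 ≈ 150,800, so the SD is about 388 mL
- Share from hematocrit: (51.8 × 3)²/150,800 = 16.0%
- Share from blood volume: (500 × 0.114)²/150,800 = 2.2%
- Left after adjusting for both: about 82%

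**Across the range.** Large-sample simulation of the same model agrees with the hand calculation to within about one percentage point of variance:

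| ρ | Variance left, hematocrit alone | Variance left, both covariates | Slope, mL per point |
|---|---|---|---|
| 0.4 | 0.78 | 0.77 | 67 |
| 0.5 | 0.84 | 0.82 | 53 |
| 0.7 | 0.94 | 0.90 | 26 |
| 0.8 | 0.98 | 0.93 | 12 |
| 0.9 | 0.999 | 0.91 | −2 |

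Two covariates with 100 women inflate the variance by about 1 + 2/95 = 1.02. The range of 0.77 to 0.93 then becomes about 0.79 to 0.95. Standard errors shrink by about 11% (√0.79 = 0.89) at best and 3% (√0.95 = 0.97) at the low end.

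**Chance imbalance.** The SE of the between-arm difference in predelivery hematocrit is 3 × √(2/50) = 0.6 points. A difference of at least one point has probability 9.6%. At ρ = 0.5 one point moves the contrast by about 53 mL, against an unadjusted SE of about 79 mL. That SE already contains this component: (53 × 0.6)²/79² = 16%, the same share as above.

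**Near-zero case.** If proportional loss is unrelated to true baseline and hematocrit is error-free, the correlation of cEBL with predelivery hematocrit is 0.00, and hematocrit adjustment gains nothing. With measurement error of 0.5 to 2 points (proportional loss mean 10%, SD 6%; blood volume SD 600 mL), hematocrit alone leaves 0.999 to 0.91. Adjusting for both covariates in a similar model (loss mean 11.4%, SD 5%) leaves 0.95 to 0.89.

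**Validity.** Simulated type I error of the unadjusted Welch test at 50 per arm was 5.2%, which is nominal.

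**The case against.** The strongest reply is that nothing here is an error. The trial is randomised, an unadjusted two-sample test keeps its type I error, and unadjusted analysis is a common and legitimate choice. That stands. A reader might infer that the planned cEBL comparison is biased or invalid; the documents do not support this.

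A reader might also take the 53 mL per point as a false difference added to the stated uncertainty. It is not. Averaged over randomisations, chance imbalance is part of the unadjusted SE. Adjustment removes that component and makes the estimate less sensitive to the imbalance actually observed.

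A third tempting reading is that precision is certainly lost by ignoring the outcome's own baseline. That needs a correlation the documents do not report. cEBL is already proportional to baseline, so hematocrit alone may contribute almost nothing. At correlations of 0.8 and above most of the gain comes from blood volume, a body-size multiplier. The ρ = 0.5 example is also favourable to the point: under it about 9% of women would have a negative calculated loss.

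Finally, cEBL is secondary, one of 44 outcome variables, and has a larger threat. The MLC arm receives 500cc of crystalloid and the FAUCS arm none, which could dilute the post-operative hematocrit in one arm only, and the timing of that sample is not stated. Adjusting for baseline values cannot remove this. The objection limits what the change delivers. It gives no reason to leave unused two covariates that are already in hand, since no scenario examined showed a meaningful loss of precision from adjusting.

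**Conclusion.** The point holds as a modest efficiency improvement on a secondary outcome. The planned comparison is valid; it probably forgoes some precision and is open to chance imbalance in the trial at hand. Under the stated assumptions, adjusting for both covariates leaves about 77% to 93% of the variance at correlations 0.4 to 0.9, before a cost of about 2%. The part owed to predelivery hematocrit runs from substantial at low correlation to nil near 0.9, and the imbalance carry-over falls with it, from about 53 mL per point at 0.5 to 26 at 0.7 and near zero at 0.9. All these figures rest on assumed hematocrit and blood-volume values. No primary conclusion depends on this point.

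**What to change.** Add one sentence to the Statistics section: cEBL will be analysed by a linear model with arm, predelivery hematocrit and calculated blood volume, using robust standard errors, and the adjusted mean difference with its 95% CI will be reported beside the raw comparison. State that the weight used in the blood-volume formula is a pre-operative value, so that the covariate cannot be affected by arm. If the data are already unblinded, label the adjusted result as not prespecified.

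The cost is two degrees of freedom (98 to 96 with 100 women) and no new data. The report should say that this adjustment does not address the difference in crystalloid filling between arms, which has to be considered separately when cEBL is interpreted.

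### The sample-size formula and inputs give 14 women per group for a 60% decrease, not the stated 45, and the stated power and sidedness conflict

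*Combined protocol and SAP*

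**What the plan says.** The sample-size paragraph of the Statistics section sizes the trial on the PMPS. Records of 80 consecutive women who had the MLC procedure in 2017 supply an approximate mean of 3.8 and SD of 2. The target is stated as "We aimed to detect a decrease of 60% in the PMPS in the FAUCS group". The formula divides a multiplier M = 17.1 by the square of 0.6 × m1/σ, where M is written with z(1−α) and z(1−β), α = 0.05 and β = 0.10. The same sentence also gives an expected power of 80%.

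The result is reported as "45 patients per group were required to detect a" "decrease of 60% in PMPS scores between the two groups". The allowance for losses comes afterwards: "Ultimately, we recruited 50 participants for each group to account for possible losses". The later paragraph on tests in the same section states: "All tests were performed as 2-tailed tests".

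**The concern.** A 60% fall from 3.8 is 2.28 points, more than one SD, and a difference that large does not need 45 women per group. Either the effect, the SD or the sample size is not the one that was used. Two further statements conflict. Power of 80% and β = 0.10 cannot both hold, and a multiplier built on z(1−α) is one-sided while the tests are two-tailed.

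What is at stake is the reading of the result, not the chance of detecting the stated effect. As written, the text implies that the trial could reliably detect only a very large reduction in pain, so a null result would seem to say little about moderate effects. It also offers a justification for enrolling more than three times as many women as its own formula requires.

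**Working it through.** **Inputs, all from the Statistics section.** m1 = 3.8; σ = 2; decrease 60%; α = 0.05; β = 0.10 with power also given as 80%; M = 17.1; stated N = 45 per group, raised to 50 for losses; two-tailed tests at 0.05.

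**The plan's own formula.**
- Difference: 0.6 × 3.8 = 2.28 points.
- Standardised difference: Ds = 2.28/2 = 1.14, and Ds² = 1.2996.
- N = 17.1/1.2996 = 13.16, so 14 per group. The stated 45 is 45/13.16 = 3.4 times this (3.2 times the rounded 14).

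**The multiplier.** With M = 2 × (zα + zβ)²:

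| Alpha 0.05 | 80% power | 90% power |
|---|---|---|
| One-sided | 12.4 | 17.1 |
| Two-sided | 15.7 | 21.0 |

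The printed 17.1 is therefore the one-sided, 90%-power value: 2 × (1.645 + 1.282)² = 17.13. The available text shows no square on the bracket; unsquared, the expression would be 5.85. Because 17.1 is itself stated, this does not affect the result.

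**Could another choice of power or sidedness explain 45?** For 2.28 points and SD 2, a two-sided t-test needs 13.1, so 14 per group, for 80% power (82.7% achieved). For 90% it needs 17.2, so 18 per group (91.3% achieved). Dividing 17.19 by 0.864, a worst-case allowance for the Mann-Whitney test, gives 19.9, so 20.

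**Could rounding of the inputs explain it?** With m1 as low as 3.75 and an SD as high as 2.5, Ds = 2.25/2.5 = 0.90 and N = 17.1/0.81 = 21.1. Reaching 45 with M = 17.1 and a 2.28-point difference needs an SD of 2.28 × √(45/17.1) = 3.70.

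**Could 60% mean a fall to 60% of the control mean?** Then the difference is 0.4 × 3.8 = 1.52 points and Ds = 0.76. The printed multiplier gives 17.1/0.5776 = 29.6, so 30. A two-sided t-test at 90% power needs 37.4, so 38. Neither is 45, and the formula prints 0.6 × m1 as the difference.

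**Working back from 45.** With M = 17.1, 45 per group corresponds to Ds = √(17.1/45) = 0.616, which is 1.23 points or 32% of 3.8. Separately, an effect of 0.6 SD (1.2 points) with two-sided 0.05 and 80% power needs 44.6, so 45, by t-test.

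**What the sample can do (two-sided 0.05, t-test, SD 2 in both groups).** Power for a 60% decrease at 45 per group is 99.96%. Detectable differences are Ds × 2 points, as a percentage of 3.8:

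| Per group | 80% power | 90% power |
|---|---|---|
| 45 | 0.597 × 2 = 1.19 points (31%) | 0.691 × 2 = 1.38 points (36%) |
| 50 | 0.566 × 2 = 1.13 points (30%) | 0.655 × 2 = 1.31 points (34%) |

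**The case against.** The arithmetic is hard to dispute, so the best defence concerns what follows from it.

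- **Over-sizing is conditional.** The trial is over-sized only if 60% was the real target. If the intended effect was nearer 32%, as 45 and the printed multiplier imply, 45 is about right. This stands: the firm conclusion is that effect, power, sidedness and N cannot all be true, and the over-sizing applies to the stated effect only.
- **The 0.6 SD explanation is not secure.** It gives 45 only with a two-sided alpha, 80% power and a t-test. With the printed multiplier it gives 17.1/0.36 = 47.5, so 48. It therefore means setting aside the printed multiplier, β = 0.10 and the printed form of Ds. This stands too; it is a conjecture for the sponsor to confirm or reject.
- **The missing square may come from the conversion of the PDF.** It should be checked against the source document and not counted as an error.
- **The power and sidedness conflicts matter little numerically.** For the 60% effect they move the t-test sample size only between about 11 and 18 per group. They are real inconsistencies, but they rank below the main discrepancy and do not explain it.
- **Recruitment is complete and no power is lost for the stated effect.** This limits the consequence to transparency and interpretation. It does not make the stated justification correct.

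**Conclusion.** The concern holds. On the plan's own formula and inputs, a 60% decrease needs 14 women per group, not 45, and no reading of power, sidedness, test or input rounding that was tried closes the gap for that effect. The power statement contradicts itself (80% against β = 0.10), and the one-sided multiplier does not match the two-tailed tests.

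The trial is not underpowered for the effect it names. At 45 per group, power is above 99.9%, and the sample has 80% power for a decrease of about 31% and 90% power for about 36%. These detectable differences assume an SD of 2 in both groups. The plan estimates that SD from MLC records only, so the figures are approximate. The origin of 45 cannot be determined from the documents. The point should be fixed, but it calls for no change in conduct.

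**What to change.** Correct the sample-size paragraph in the Statistics section:

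1. Identify and disclose the inputs that actually produced 45. If 0.6 SD was entered in place of 60%, say so; the sponsor must confirm this from its own records.
2. State one power figure and a two-sided alpha, with z(1−α/2) in the formula.
3. Remove the claim that a 60% decrease required 45 per group. If 60% remains the declared target, give the number that goes with it (14 per group for 80% power, 18 for 90%) and do not present it as the reason for the enrolment.
4. Add a sentence marked as calculated afterwards and not as the design target. Suggested wording: *Sensitivity of the enrolled sample (calculated afterwards, not the design target): with SD 2 in both groups, two-sided alpha 0.05 and 45 evaluable women per group, the trial has 80% power for a difference of about 1.2 points (31% of 3.8) and 90% power for about 1.4 points (36%).*
5. Check the expression for M against the source document and add the square if it is missing there.

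The cost is wording only: no extra patients and no change to the analysis.
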